4.4.1.1.2 Maximum Overall Intensity

Maximum overall intensity is derived from the daily intensities computed as described in Section 4.4.1.1.1 and is calculated as the maximum of the daily intensities over the period considered.

4.4.1.1.3 Presence

Presence is derived from the maximum overall intensity on the period considered:

- None: No presence
- Grade 1, Grade 2, or Grade 3: Presence
- Missing: Missing presence

Subjects with at least one non-missing presence for a specific endpoint will be included in the analysis. Conversely, those without a non-missing presence will not be included in the analysis of the endpoint.

4.4.1.1.4 Time of Onset

Time of onset is derived from the daily intensities computed as described in Section 4.4.1.1.1. It corresponds to the first day with intensity of Grade 1, Grade 2, or Grade 3.

Note: If a reaction is not continuous (i.e., reaction occurs over two separate periods of time intervened by at least one daily intensity Missing or None) then the time of onset is the first day of the first occurrence.

4.4.1.1.5 Number of Days of Occurrence

Number of days of occurrence over the period considered is derived from the daily intensities computed as described in Section 4.4.1.1.1. It corresponds to the number of days with daily intensities of Grade 1, Grade 2, or Grade 3. Number of days of occurrence on the solicited period with a specified intensity may also be derived.

4.4.1.1.6 Overall Number of Days of Occurrence

If a reaction is ongoing at the end of the solicited period, then the overall number of days of occurrence is derived from the daily intensities and the stop date of the reaction after the end of the solicited period. The overall number of days of occurrence is:

- (stop date – last vaccination date) + (number of days of occurrence within the solicited period) – length of the solicited period + 1

If the stop date is missing or incomplete (contains MD), the overall number of days of occurrence will be considered as Missing.

4.4.1.1.7 Ongoing

Ongoing is derived from the last daily intensity of the solicited period computed as described in Section 4.4.1.1.1 and the maximum intensity on the ongoing period. The investigator's ongoing flag is not used because the measurement would determine the ongoing status of the reaction.

If the last daily intensity of the solicited period is at least Grade 1 and maximum intensity on the ongoing period is also at least Grade 1, then the reaction is considered ongoing. In any other cases the reaction will not be considered as ongoing.

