4.3.2.3.3 Unsolicited Non-serious Adverse Events From Day 0 to Day 30 After Vaccination

In addition to recording solicited reactions, subjects or parents / guardians will be instructed to record any other medical events that may occur during the 30-day period after vaccination. Space will be provided in the diary card for this purpose.

For each unsolicited non-serious AE, the following information is to be recorded:

- Start and stop dates^a
- Intensity of the event:
 - For measurable unsolicited non-serious AEs that are part of the list of solicited reactions, the size of the AE as well as the temperature for fever will be collected and analyzed based on the corresponding scale used for solicited reactions (see Table 4.1 and Table 4.2)
 - Other unsolicited non-serious AEs will be classified according to the following intensity scale:
 - Grade 1: No interference with activity
 - Grade 2: Some interference with activity
 - Grade 3: Significant; prevents daily activity
- Action taken for each AE, if any (e.g., medication)

The action taken by the subject or parent / guardian to treat any **unsolicited AEs** will be classified in the CRF using the following scale:

- 0: None
- 1: Medication (self-medication with an existing prescription or over-the-counter medication)
- 2: Health care provider contact (no new medication prescribed)
- 3: Health care provider contact and prescription of a new medication (health care provider instructed subject to take a new medication, either an over-the-counter medication or one requiring a written prescription)

^a The stop date of all related AEs will be actively solicited. For other events, the investigator will provide the stop date when it becomes available. AEs for which no stop date was obtained during the course of the trial will be considered as ongoing at the end of the trial.

- Whether the AE led to discontinuation
- Whether the AE was related to vaccination (for unsolicited systemic AEs)

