4.4 Derived Endpoints: Calculation Methods

4.4.1 Safety

4.4.1.1 Solicited Reactions

4.4.1.1.1 Daily Intensity

All daily records for solicited reactions will be derived into daily intensity according to the following classification: None, Grade 1, Grade 2, Grade 3, or Missing.

For the derivation of daily intensities the following sequential steps will be applied:

- 1) Solicited reactions (except Fever/Pyrexia) with an investigator presence recorded as “No” and with all daily records missing then all daily intensities will be derived as None.
- 2) For a temperature partially missing after decimal point, the data will be analyzed replacing “MD” (missing data) by zero. For example, a “39.MD” daily temperature will be considered as "39.0°C" at the time of analysis.
- 3) For non-measurable (NM) solicited reactions, daily intensities will correspond to daily records reported in the clinical database. For measurable solicited reactions the daily measurements reported in the clinical database will be converted based upon the intensity scales defined in the protocol; this assumes a reaction that is too large to measure (NM) is Grade 3. Note the intensity could be considered “None” (not a reaction) in the analysis despite being considered a reaction by the investigator (e.g., swelling measurement > 0 mm but < 25 mm in adults).

Note: The maximum intensity on the ongoing period is derived from the record of the maximum intensity/measurement after the end of the solicited period following the rule described above.

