4.4.1.2.5 Duration

Duration is derived from the start and stop dates of the unsolicited non-serious AE provided in the clinical database:

- stop date of unsolicited non-serious AE - start date of unsolicited non-serious AE + 1.

The duration should be considered as missing only if one or both of the start and stop dates of the unsolicited non-serious AE is missing or partially missing.

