5.3 Handling of Missing Data and Outliers

5.3.1 Safety

No replacement will be done. In all subject listings, partial and missing data will be clearly indicated as missing.

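### Missing intensities are read as 'not ongoing' and absent stop dates as 'Missing' durations, so the descriptive duration summaries lean short

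*SAP*

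**What the plan says.** **Ongoing status (SAP 4.4.1.1.7).** Two conditions must both hold, and the threshold cut off at the end of this quote is the same as the first one: "If the last daily intensity of the solicited period is at least Grade 1 and maximum intensity on the ongoing period is also at least". Everything else goes to a single default: "In any other cases the reaction will not be considered as ongoing". The investigator's own entry is set aside: "The investigator's ongoing flag is not used because the measurement would determine the ongoing status of the reaction".

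**Intensity values (SAP 4.4.1.1.1).** Daily records are reduced to this "classification: None, Grade 1, Grade 2, Grade 3, or Missing". The maximum after the solicited period is derived by the same rule, so either input to the ongoing test can be Missing.

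**Days and duration.**
- SAP 4.4.1.1.6 gives a formula for the overall number of days of an ongoing reaction and then says: "If the stop date is missing or incomplete (contains MD), the overall number of days of occurrence will be considered as Missing".
- SAP 4.4.1.2.5, for unsolicited non-serious AEs, makes the result depend on whether a date is absent or partial: "The duration should be considered as missing only if one or both of the start and stop dates". SAP 4.4.1.3.3 applies the same method to SAEs, and SAP 4.4.1.4 applies it to MAAEs.
- SAP 5.3.1.5 rules out imputing stop dates.

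**What an absent stop date means.** The footnote in SAP 4.3.2.3.3 (also in Protocol 9.3.2.3.3), speaking of status when the trial ends, says: "AEs for which no stop date was obtained during the course of the trial will be considered as ongoing". It also says that stop dates are actively sought for related AEs; other stop dates are supplied when they become available.

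**Outputs.** SAP 4.3.2.2 lists number of days of occurrence for solicited reactions, and duration for immediate unsolicited AEs, unsolicited AEs, SAEs and MAAEs. Table 5.2 also lists duration for solicited reactions.

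**The concern.** There are two separate faults.

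The first is a classification that does not follow from the data. A blank grade on D07, or after it, is an unknown. The catch-all turns it into a no, even where a recorded stop date shows that the reaction outlasted D07. SAP 4.4.1.1.3 handles the same situation for presence by keeping a Missing outcome, and SAP 5.3.1 states the general principle for safety data: "No replacement will be done". The ongoing rule departs from both. The stated reason for ignoring the flag, that a measurement settles the matter, fits redness, swelling and fever. It does not fit pain, headache, malaise or myalgia, four of the seven solicited reactions, for which the subject records a grade and nothing is measured.

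The second is the handling of unresolved events. When an event has no stop date because it has not ended, what is known is a lower bound on its duration. The SAP discards that bound and records Missing. Summaries of the remaining durations then describe events that ended and were dated.

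At stake is how persistence is described in the safety report: how many reactions outlast the diary period, and how long events last.

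**Working it through.** The documents give no figure for duration or ongoing status, so there is none to reproduce. The rules can be run on a case, and the direction of the effect can be illustrated under stated assumptions.

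**Solicited reactions**

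Inputs: the solicited period is D0 to D07, which is 8 calendar days (SAP 4.3.2.3.2). The test in SAP 4.4.1.1.7 requires both grades. The formula in SAP 4.4.1.1.6 is

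overall days = (stop day − vaccination day) + graded days in the solicited period − length of the period + 1.

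Take a reaction of Grade 2 on every day from D0 to D20. Its true length is 21 days.

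| Case | What is recorded | Ongoing under 4.4.1.1.7 | Result |
|---|---|---|---|
| A | All grades, stop D20 | Yes | 20 + 8 − 8 + 1 = 21 |
| B | All grades, stop date missing | Yes | Overall days Missing; 8 days in the solicited period |
| C | Post-D07 grade missing, stop D20 | No | 8 days remain |
| D | D07 grade missing, post-D07 Grade 2, stop D20 | No | 7 days remain |

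Case A confirms that the formula is right when the data are complete and the length is 8; a length of 7 would give 22. In C and D a stop date of D20 is on file, yet the reaction is declared not ongoing. The SAP gives no overall-days formula for a reaction that is not ongoing, so the solicited-period count is taken as what remains. If case D were instead accepted as ongoing, the formula would give 20 + 7 − 8 + 1 = 20, not 21, because the blank D07 is not counted.

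**Unsolicited AEs, SAEs and MAAEs**

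Here the check is to set the sections side by side. SAP 4.3.2.3.3 reads an absent stop date on a non-serious AE as unresolved at trial end. SAP 4.4.1.2.5 reads the same absence as Missing duration, and 4.4.1.3.3 and 4.4.1.4 carry that rule to SAEs and MAAEs. No section presents such events as censored or with a minimum duration.

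To illustrate, one million durations were simulated per row. Every distributional input is an assumption: log-normal durations rounded up to whole days, onset uniform over D0 to D30, and duration set to Missing if the event is unresolved at the cut-off. D187 is the middle of the 180 to 194 day follow-up window; D37 is the middle of the 30 to 44 day Visit 2 window.

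| Assumed median, log-SD | Cut-off | Missing | Mean, true → observed | Median, true → observed |
|---|---|---|---|---|
| 5 days, 1.0 | D187 | 0.0% | 8.7 → 8.7 | 6 → 6 |
| 7 days, 1.2 | D187 | 0.4% | 14.9 → 13.9 | 8 → 7 |
| 10 days, 1.5 | D187 | 2.9% | 31.4 → 21.3 | 11 → 10 |
| 14 days, 1.5 | D187 | 4.7% | 43.7 → 26.3 | 14 → 13 |
| 5 days, 1.0 | D37 | 9.5% | 8.7 → 6.5 | 6 → 5 |
| 7 days, 1.2 | D37 | 19.5% | 14.9 → 7.6 | 8 → 6 |
| 10 days, 1.5 | D37 | 31.8% | 31.4 → 8.1 | 11 → 6 |
| 14 days, 1.5 | D37 | 39.6% | 43.7 → 9.0 | 14 → 7 |

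If stop dates are obtained through the six-month contact, the median moves by at most 1 day and the mean suffers only when the tail is heavy. If they are in practice obtained only to about Visit 2, the loss is much larger. The documents do not say which is closer to practice.

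**The case against.** Much can be said for the plan.

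- **Nothing is removed from the main solicited endpoint.** Number of days of occurrence counts graded days (SAP 4.4.1.1.5) and needs neither ongoing status nor a stop date. A reaction classed as not ongoing still counts for presence, onset and intensity. This stands.
- **Ignoring the flag has a purpose.** SAP 4.4.1.1.1 notes that an investigator may record a reaction that the analysis grades as None, such as swelling under 25 mm. Using the flag for measured reactions could bring those back. This stands, and it limits the fix.
- **Ongoing and Missing are not contradictory.** An event can be unresolved and have no calculable duration. The stop-date footnote also sits in the section on non-serious AEs, so it says nothing directly about SAEs, whose outcome is tabulated. Both points are fair. The objection is to discarding the known minimum, not to a logical conflict.
- **Collection safeguards exist.** Missing or discrepant diary data are clarified with the subject (Protocol 13.2), and AEs likely to be product-related that persist at trial end are followed to disappearance or stabilization (SAP 4.3.2.3.7). These reduce the number of affected events and push the loss of stop dates towards unsolicited AEs judged unrelated. They do not change what the rule does with a value that stays missing.
- **The table shells are not in the documents.** Counts of unresolved events may already be planned there. If so, the second part of the fix is already met.

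A reader might infer that the longest-lasting events drop out of the duration endpoints. The documents do not support that. A long AE with complete dates keeps its full duration, and a misclassified solicited reaction is shortened rather than dropped. Only an event without complete dates loses its duration.

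**Conclusion.** The concern holds as a fault in two derivation rules, confined to descriptive safety output. In identifiable cases SAP 4.4.1.1.7 gives an answer that the recorded data contradict, leaving 8 or 7 days of a 21-day reaction. Where stop dates are absent, duration summaries rest on events that ended and were dated, and so lean short.

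The direction rests on reading an absent stop date as an unresolved event, which is the SAP's own reading for non-serious AEs. The shortening to 8 or 7 days rests on the solicited-period count being what is reported for a reaction that is not ongoing. The size cannot be established: the documents give no rate of missing D07 or post-D07 grades and no expected durations, and the simulated range depends entirely on its assumptions. Safety is observational with no hypotheses tested (SAP 5.1.3.1), so no primary or secondary conclusion changes. This is a worthwhile correction, not a serious one.

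**What to change.** **SAP 4.4.1.1.7.** When the D07 or post-D07 intensity is missing:
- for pain, headache, malaise and myalgia, classify the reaction as ongoing if its stop date is after D07 or the investigator flagged it as ongoing, unless the recorded grades contradict this;
- for redness, swelling and fever, report ongoing status as Missing rather than as not ongoing, so that sub-threshold reactions are not brought back through the flag.

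**SAP 4.4.1.1.6, 4.4.1.2.5 and 4.4.1.3.3, and the MAAE summaries that use the same method.** In the duration tables, show by group the number of events without a stop date as ongoing at last contact, at least k days, where k runs to the last contact or last graded day. Events with a partial stop date have ended and should stay in a separate Missing row.

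**Cost.** SAP wording and one extra category in descriptive tables. The rules already refer to the grades, stop dates and investigator flag, so no new data collection is needed.

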4.4.1.2 Unsolicited Non-serious AEs

4.4.1.2.1 Presence

An observation will be considered an event if it has at least a verbatim term and is not a Grade 0 intensity event. Grade 0 events should be included in the listing “Unsolicited non-serious adverse events not included in the safety analysis.”

4.4.1.2.2 Intensity

Intensity for unsolicited non-serious AE will be derived according to the following classification: None, Grade 1, Grade 2, Grade 3, or Missing.

If the unsolicited non-serious AE is measurable and its preferred term is part of the list of solicited reactions, then the measurement is derived based upon and following the same rule than the intensity scales defined in the protocol for that measurable injection site or systemic reaction.

Intensity for the other unsolicited non-serious AEs will correspond to the value reported in the CRF.

The maximum intensity corresponds to the highest intensity for a unique term.

4.4.1.2.3 Last Vaccination

Last vaccination before any unsolicited non-serious AE is the study vaccination at Visit (V) 01.

4.4.1.2.4 Time of Onset

Time of onset is derived from the start date of the unsolicited non-serious AE provided in the clinical database and the date of last vaccination:

- start date of the unsolicited non-serious AEs – date of previous vaccination

The time of onset should be considered as missing only if one or both of the dates are missing or partially missing.

The unsolicited non-serious AEs will be analyzed “Within 30 days”, which corresponds to AEs with a time of onset between 0 and 30 days after vaccination or missing. An AE with missing time of onset will be considered to have occurred just after the vaccination indicated by the visit number, so will be included in these tables.

Note: Unsolicited non-serious AEs that occurred before vaccination (negative time of onset) or with a time of onset higher than defined above will not be included in analysis, but will be listed separately.

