### 9.3.2.2 Safety Endpoints

The observational endpoints for the evaluation of safety are:

- Occurrence, nature (Medical Dictionary for Regulatory Activities [MedDRA] preferred term), duration, intensity, and relationship to vaccination of any unsolicited systemic AEs reported in the 30 minutes after vaccination.
- Occurrence, time of onset, number of days of occurrence, intensity, action taken, and whether the reaction led to early termination from the study, of solicited (prelisted in the subject's diary card and electronic case report form [CRF]) injection site reactions occurring up to 7 days after vaccination.
- Occurrence, time of onset, number of days of occurrence, intensity, action taken, and whether the reaction led to early termination from the study, of solicited (prelisted in the subject's diary card and CRF) systemic reactions occurring up to 7 days after vaccination.
- Occurrence, nature (MedDRA preferred term), time of onset, duration, intensity, action taken, relationship to vaccination (for systemic AEs only), and whether the event led to early termination from the study, of unsolicited AEs up to Visit 2 after vaccination.
- Occurrence, nature (MedDRA preferred term), time of onset, duration, seriousness criteria, relationship to vaccination, outcome, and whether the SAE led to early termination from the study, of SAEs throughout the trial.
- Occurrence, nature (MedDRA preferred term), time of onset, duration, seriousness, relationship to vaccination, and outcome for MAAEs from Visit 2 to the 6-month follow-up contact. MAAEs will be collected as unsolicited AEs up to Visit 2.

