### 12.1.3.2 Safety

Safety results will be described for subjects in all study groups. The main parameters for the safety endpoints will be described by 95% CIs (based on the Clopper-Pearson method).

The frequency and percentage of subjects who had solicited injection site and systemic reactions and their 95% CIs will be provided. These events will be tabulated by type of reactions and intensity for each study group, as well as by other categories specified in the endpoints.

Unsolicited AEs will be collected, coded, and summarized by MedDRA system organ class and preferred term. For each unsolicited AE, the number of subjects with at least one instance of that event will be reported. Unsolicited AEs will also be tabulated by other categories specified in the endpoints.

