3.1 Trial Design

This is a Phase III, modified double-blind, randomized, parallel-group, active-controlled, multi-center study to evaluate immune lot consistency of MenACYW conjugate vaccine, evaluate the immune non-inferiority versus Menactra[®], and describe the safety and additional immunogenicity of these study vaccines in adolescents and adults aged 10 to 55 years in the United States.

Healthy, meningococcal-vaccine naïve adolescents and adults will be randomized in a 3:3:3:2 ratio to the following groups:

- Group 1: MenACYW conjugate vaccine (Lot 1)
 - Group 1a: 400 subjects 10 to 17 years of age
 - Group 1b: 500 subjects 18 to 55 years of age
- Group 2: MenACYW conjugate vaccine (Lot 2)
 - Group 2a: 400 subjects 10 to 17 years of age
 - Group 2b: 500 subjects 18 to 55 years of age
- Group 3: MenACYW conjugate vaccine (Lot 3)
 - Group 3a: 400 subjects 10 to 17 years of age
 - Group 3b: 500 subjects 18 to 55 years of age
- Group 4: Menactra[®]
 - Group 4a: 300 subjects 10 to 17 years of age
 - Group 4b: 300 subjects 18 to 55 years of age

All subjects will provide blood samples for immunogenicity assessment at baseline (pre-vaccination) and at 30 to 44 days post-vaccination.

Solicited adverse event (AE) information will be collected for 7 days after vaccination, unsolicited AE information will be collected from Visit 1 (Day [D] 0) to Visit 2 (D30 [+14 days]), and serious adverse event (SAE) information will be collected from D0 through D180 (+14 days) after vaccination.

Medically-attended adverse events (MAAEs) information will be collected throughout the study from Visit 1 to Visit 2 (as part of the collection of unsolicited AE information) and from Visit 2 through D180 (+14 days) (as MAAEs).

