**This call is made 8 to 10 days after the vaccination at Visit 1. If D08 (+2 days) falls on a weekend or holiday, the telephone call may be made on the following business day. During this telephone call, the staff will find out whether the subject experienced any SAE not yet reported, and will remind the subject / subject's parent / guardian to continue using the diary card up to Visit 2, to bring the diary card to the study center at Visit 2, and confirm the date and time of Visit 2.

††Staff will contact the subject / subject's parent / guardian by telephone at 6 months (180 days +14 days) after vaccination at Visit 1 to identify the occurrence of any MAAEs as well as SAEs not yet reported.

‡‡MAAEs that occur between Visit 1 and Visit 2 will be recorded as unsolicited AEs.

§§The MA is used for the recording of SAEs and MAAEs. The site staff will make a telephone call to the subject/subject's parent / guardian to obtain the information 180 days (+14 days) after the vaccination at Visit 1. Since the timeframe between Visit 1 and Visit 2 (inclusive) will be captured in the diary card, the MA will be used to collect SAE and MAAE data from Visit 2 to TC2.

Vaccination

All subjects will receive a single dose of MenACYW conjugate vaccine (from 1 of the 3 lots [Lot 1, Lot 2, or Lot 3]) or Menactra[®] on D0.

Blood sampling

All subjects will provide a pre-vaccination blood sample at D0 and a post-vaccination sample at Visit 2 (30 to 44 days after the vaccination at Visit 1).

A, C, Y, and W antigens of MenACYW conjugate vaccine (Groups 1, 2, and 3) and Menactra[®] (Group 4) will be measured by hSBA for all subjects, and by serum bactericidal assay using baby rabbit complement (rSBA) for a subset of 100 subjects per treatment group.

Collection of safety data

- All subjects will be observed for 30 minutes after vaccination, and any unsolicited systemic AEs occurring during that time will be recorded as immediate unsolicited systemic AEs in the electronic case report form (CRF).
- The subject or the subject's parent / guardian will record information in a diary card about solicited reactions from D0 to D07 after vaccination and unsolicited AEs from D0 to Visit 2. SAEs will be reported throughout the duration of the trial.
- The subject or the subject's parent / guardian will record information about any possible SAEs and MAAEs in a memory aid (MA) from Visit 2 until the 6 month (+14 days) telephone call.

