4.4.4.3 Duration of the Study

The duration of the study (until last visit) is computed as follows: Maximum of all subjects (date of last visit, date of termination form) – minimum for all subjects (date of Visit 1) +1.

The duration of the study (including follow-up) is computed as follows: Maximum of all subjects (date of last visit, date of termination form, date of last follow-up contact) – minimum for all subjects (date of Visit 1) +1

4.4.4.4 MAAEs from Visit 1 to Visit 2

MAAEs that occur from Visit 1 to Visit 2 will be recorded as unsolicited AEs on the diary card as part of all unsolicited AEs collected for this post-vaccination period. The unsolicited AEs that have action taken categories 2 (health care provider contact) or 3 (Health care contact + Medication) will be summarized and presented as MAAEs which occurred from Visit 1 to Visit 2.

5 Statistical Methods and Determination of Sample Size

The statistical analyses will be performed under the responsibility of the Sponsor's Biostatistics platform using SAS® Version 9.4 software or later.

The results of the statistical analysis will be available in the final clinical study report (CSR).

For descriptive purposes, the following statistics in Table 5.1 will be presented. The confidence interval (CI) for the single proportion will be calculated using the exact binomial method (Clopper-Pearson method, quoted by Newcombe (7)). For immunogenicity results, assuming that Log₁₀ transformation of the titers / data follows a normal distribution, at first, the mean and the 95% CI will be calculated on Log₁₀ (titers / data) using the usual calculation for normal distribution (using Student's t distribution with n-1 degree of freedom), then antilog transformations will be applied to the results of calculations, in order to provide geometric means (GMs) and their 95% CI.

Table 5.1: Descriptive statistics produced

Baseline characteristics and follow-up description	Categorical data	Number of subjects. Percentage of subjects.
	Continuous data	Mean, standard deviation, quartiles, minimum, and maximum.
Clinical safety results	Categorical data	Solicited: Number and percentage (95% CIs) of subjects. Unsolicited: Number and percentage (95% CIs) of subjects, and number of events.
Immunogenicity results	Categorical data (seroresponse, cutoff)	Number and percentage (95% CIs) of subjects.

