5.1.3.2.2 Safety

Safety results in Section 4.3.2.2 will be described for subjects in all study groups. The main parameters for the safety endpoints will be described by 95% CIs (Clopper-Pearson method) (7). Analyses will contain at least the descriptions listed in Table 5.2:

Table 5.2: Statistical analyses for safety observational objective

Safety Events	Time and Group	Description
Immediate unsolicited systemic AE	Within 30 minutes after injection for all subjects in Groups 1 - 4 at D0	Proportion of subjects that have the event, MedDRA terms, intensity, relationship to vaccine, study discontinuation, duration
Solicited injection site reactions	Up to 7 days after D0 for all subjects in Groups 1 - 4	Proportion of subjects that have the event, time of onset, duration, intensity, action taken, study discontinuation, number of days of occurrence, temperature collection routes
Solicited systemic reactions	Up to 7 days after D0 for all subjects in Groups 1 - 4	
Unsolicited AE	Up to 30 days after D0 for all subjects in Groups 1 - 4	Proportion of subjects that have the event, MedDRA terms, time of onset, duration, intensity, relationship, action taken, study discontinuation
SAE	Up to 6-month follow-up after D0 for all subjects in Groups 1 - 4	Proportion of subjects that have the event, MedDRA terms, time of onset, duration, relationship, seriousness criteria, outcome, study discontinuation
MAAE	Between Visit 1 and Visit 2 for all subjects in Groups 1 - 4 (as unsolicited AE) From Visit 2 to 6-month follow-	Proportion of subjects that have the event, MedDRA terms, time of onset, duration, intensity, relationship, action taken, outcome, study discontinuation

	up contact for all subjects in Groups 1 - 4	
--	---	--

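### The unsolicited AE endpoint and data collection run to Visit 2 (Day 30–44), but the SAP's unsolicited AE tables stop at onset on Day 30, and its MAAE window before Visit 2 is stated inconsistently

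*SAP*

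**What the plan says.** **Endpoint.** Protocol 9.3.2.2 and SAP 4.3.2.2 carry the same text. The attributes to be described end with "whether the event led to early termination from the study, of unsolicited AEs up to Visit 2 after vaccination". The protocol synopsis agrees.

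**Collection.** Protocol 5.1.1 and SAP 3.1 agree: "unsolicited AE information will be collected from Visit 1 (Day [D] 0) to Visit 2 (D30 [+14 days"]). Visit 2 is 30 to 44 days after vaccination (Protocol 5.1.3, SAP 3.2). A footnote to SAP Table 3.1 confirms the diary coverage: "Since the timeframe between Visit 1 and Visit 2 (inclusive) will be captured in the diary card".

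**Analysis.** SAP 4.4.1.2.4 defines the reporting window as onset 0 to 30 days after vaccination, or onset missing. Events before vaccination, or "with a time of onset higher than defined above will not be included in analysis, but will be listed separately". The unsolicited AE row of SAP Table 5.2 (section 5.1.3.2.2) reads "Up to 30 days after D0 for all subjects in Groups 1 - 4".

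**30-day wording elsewhere.** Protocol 9.3.2.3.3 and SAP 4.3.2.3.3 are headed Day 0 to Day 30 and have subjects record events over a 30-day period. Protocol 6.7 gives a 30-day safety follow-up as its example.

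**MAAEs before Visit 2.** These are unsolicited AEs with action taken category 2 or 3. SAP 4.4.4.4 says they "will be summarized and presented as MAAEs which occurred from Visit 1 to Visit 2", and the MAAE row of Table 5.2 says "Between Visit 1 and Visit 2 for all subjects in Groups 1 - 4 (as unsolicited AE"). SAP 4.4.1.4 instead says they are presented between D0 and D30, and applies the calculation methods of section 4.4.1.2 to them.

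**The concern.** An endpoint stated in both documents is not fully summarised by the analysis planned for it. A dated, non-serious event with onset between Day 31 and the subject's Visit 2 is within the endpoint and within the diary period, but it is left out of the unsolicited AE tables. The listing it goes to gives no proportion or confidence interval by group, and these are what the SAP plans for unsolicited AEs in Table 5.1.

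The MAAE passages add a second difficulty. MAAEs before Visit 2 are a subset of the unsolicited AEs, taken from the same diary. If the subset and its parent category are cut at different days, a reader of the study report cannot trace one table to the other.

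**Working it through.** No planned figure needs reproducing here. The check is a comparison of windows followed by a count of days.

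**1. Windows side by side**

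| Item | Source | Window |
|---|---|---|
| Endpoint | Protocol 9.3.2.2; SAP 4.3.2.2 | to Visit 2 |
| Collection | Protocol 5.1.1; SAP 3.1; both procedure tables | Visit 1 to Visit 2 |
| Diary coverage | SAP 3.2, Table 3.1 footnote | Visit 1 to Visit 2, inclusive |
| Recording instruction | Protocol 9.3.2.3.3; SAP 4.3.2.3.3 | 30 days |
| Analysis, unsolicited non-serious AEs | SAP 4.4.1.2.4; Table 5.2 | onset Day 0–30 (4.4.1.2.4 adds missing onset) |
| Analysis, SAEs | SAP 4.4.1.3.2 | whole study, and within 30 days |

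The endpoint, design, diary and procedure-table text all point to Visit 2. One subsection in each document points to 30 days, and the analysis follows that subsection.

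**2. Days collected but not tabulated**

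Let V be the day of Visit 2, from 30 to 44. Counting Day 0:

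- collected days = V + 1
- tabulated days = 31 (Day 0 to Day 30)
- days left out = V − 30
- share left out = (V − 30) / (V + 1)

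| Visit 2 | Collected | Left out | Share |
|---|---|---|---|
| Day 30 | 31 | 0 | 0% |
| Day 37 | 38 | 7 | 7/38 = 18.4% |
| Day 44 | 45 | 14 | 14/45 = 31.1% |

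The documents give no distribution of Visit 2 dates. If they were spread evenly over the 15 possible days (an assumption), the overall share would be (0 + 1 + … + 14) / (31 + 32 + … + 45) = 105/570 = 18.4%. Within-window visits bound the share between 0% and 31.1%.

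These are shares of calendar time, not of events. Without AE rates by day, the change in any AE percentage cannot be derived.

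**3. A worked MAAE case**

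Take a non-serious unsolicited AE with onset on Day 35, action taken category 2, in a subject whose Visit 2 is on Day 40.

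- Under SAP 4.4.4.4 and Table 5.2, it is in the MAAE table but not in the unsolicited AE table.
- Under SAP 4.4.1.4 read literally, it is in neither table. That section limits the presentation to D0–D30 and refers to section 4.4.1.2, which contains the Day 30 exclusion. It then assigns D30 to D180 events to the memory aid, but the memory aid is handed out only at Visit 2.

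SAP 4.4.1.4 does not settle the matter itself. Its first sentence describes collection to D30 (+14 days), so D30 in the next sentence could be shorthand for Visit 2. The imported calculation methods could also mean only the derivation formulas, but the text does not say so.

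**The case against.** The best defence is that the 30-day window is pre-specified, is identical in all arms and gives every subject the same observation time. It also has a basis in the protocol, because section 9.3.2.3.3 describes a 30-day recording period. Later events are listed rather than discarded, SAEs are summarised for the whole study, and safety carries no hypothesis. All of that stands. It justifies keeping the 30-day table, but it does not explain why the endpoint as written has no summary. The SAP already handles the same choice for SAEs by reporting two periods.

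Several stronger readings are tempting but not supported:

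- *The SAP made an undeclared change, because section 5.7 says not applicable.* The protocol contains both windows and the SAP follows one of them, so this inference is weak.
- *The protocol promises a table to Visit 2.* Protocol 12.1.3.2 says "Unsolicited AEs will also be tabulated by other categories specified in the endpoints". This most naturally means the attributes in the endpoint, such as intensity, action taken and relationship. The section names no time window.
- *The MAAE and unsolicited AE tables will fail to reconcile.* They may. Under SAP 4.4.1.4 read literally, both stop at Day 30 and agree.
- *Late events appear only in a listing.* Not necessarily. Under SAP 4.4.4.4 the medically-attended ones are tabulated as MAAEs. The disposition table in SAP 4.4.1.5.6 counts terminations for an adverse event without a Day 30 limit.
- *The comparison between vaccines is biased.* Nothing in the documents suggests this. The same rule applies to all four groups.

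**Conclusion.** The point holds as one of incompleteness and internal inconsistency. Followed as written, the SAP leaves dated non-serious events from Day 31 to Visit 2 out of the unsolicited AE tables, although they belong to the endpoint in both documents. The gap is 0 to 14 days per subject, provided Visit 2 takes place within its window. The SAP separately contradicts itself on the window for MAAEs before Visit 2, so whether a late MAAE is tabulated depends on which section the programmer follows.

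The primary and secondary immunogenicity objectives, the error rate and the power are untouched. The matter deserves correction because a stated safety endpoint is only partly summarised and the data to complete it are already collected.

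**What to change.** 1. In SAP 4.4.1.2.4 and the unsolicited AE row of Table 5.2, keep the 30-day summary. Add a summary of unsolicited non-serious AEs with onset from vaccination to the subject's own Visit 2 date.
2. State the cut-off for subjects with no Visit 2. They may still return a diary card, since Protocol 5.1.4 has sites ask for it.
3. Reconcile the 30-day wording in Protocol 9.3.2.3.3 and SAP 4.3.2.3.3 with the Visit 2 endpoint.
4. Reconcile SAP 4.4.1.4 with SAP 4.4.4.4 and the MAAE row of Table 5.2, so that one window applies to MAAEs before Visit 2. Say whether the reference to section 4.4.1.2 covers the reporting window or only the derivation formulas.

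The cost is some wording and one added table period, with no new data. The drawback is that observation time in the added table varies between subjects with the date of Visit 2. The 30-day table remains as the constant-window summary.
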